1.4.2 Secondary objectives

- 1. Assess mortality on days 7, 14 and 28 after hospitalization;
- 2. Evaluate indicators of clinical worsening (use of supplemental oxygen, ICU stay, length of stay in the ICU, length of hospital stay, need for intubation and time on mechanical ventilation, radiological alterations and time to improve the radiological and resonance pattern);
- 3. Assess the percentage of SARS-CoV2 detection in oropharyngeal swab, nasal and blood swab samples on days 1, 3, 5, 8, 11, 14 and 28, in the study population;

- 4. Quantify the virus that causes SARS-CoV2 in oropharyngeal swab, nasal and blood swab samples on days 1, 3, 5, 8, 11, 14 and 28, in the study population;
- 5. Cumulative incidence of adverse events (AEs);
- 6. Cumulative incidence of grade 3 and 4 serious adverse events (SAEs);
- 7. Discontinuation or temporary suspension of treatment (for any reason);
- 8. Alterations in white cell count, hemoglobin, platelets, creatinine, glucose, total bilirubin, ALT and AST over time;
- 9. In case of mortality, describe organic alterations via autopsy.

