1.12 Table 1: Schedule for evaluation throughout the study

| Description of the procedures according | D0* | D1∞ | D2 | D3 | D4 | D5 | D6 | D7 | D8 | D9 | D10 | D11 | Dx | D14# | D28# |
|--|-----|-----|-----|-----|-----|-----|-----|-----|-----|-----|-----|-----|-----|------|------|
| to the protocol $^{\mu}$ | D0 | Di | D2 | D3 | | | 20 | 2, | | | DIO | | | | D20 |
| Application of ICF ^t | X | | | | | | | | | | | | | | |
| Review of eligibility criteria ^a | X | | | | | | | | | | | | | | |
| Randomization ^b | X | | | | | | | | | | | | | | |
| Demography, medical history, including comorbidities (HAS, DM, dG6PD) and coinfections (HIV, TB, hepatitis) ^c | X | | | | | | | | | | | | | | |
| Physical exam ^d | X | | | | | | | | | | | | | | |
| Clinical evaluation ^e | X | X | X | X | X | X | X | X | X | X | X | Х | X | X | X |
| Evaluation of concomitant medication ^f | X | X | X | X | X | X | X | X | X | X | X | X | X | X | X |
| 12-lead ECG ^g | X | X | X | X | X | X | X | X | Х | X | X | X | X | X | X |
| Blood sample collection for hematology and biochemistry ^h | Х | (x) | (x) |
| Blood sample collection for virology and storage ⁱ | Х | Х | | X | | Х | | X | | | | Х | X | Х | Х |
| Oropharyngeal Swab and Nasal Swab | Х | X | | X | | X | | X | | X | | Х | X | X | X |
| Record of adverse events (serious and non-serious) ^j | X | X | X | X | Х | Х | Х | X | X | X | X | X | X | X | Х |
| Assessment of the primary outcome ^k | | | | | | | | X | | | | | | X | X |
| Record of secondary outcomes ¹ | | X | X | X | X | X | X | X | X | X | X | X | X | X | Х |

Version_2.0_23march2020

| Respiratory evaluation ^m | (x) |
|--------------------------------------|-----|-----|-----|-----|-----|-----|-----|-----|-----|-----|-----|-----|-----|-----|-----|
| Radiological evaluation ⁿ | (x) |

- μ All data from the study procedures will be collected and entered into the RedCap system;
- * Screening and Randomization may occur on the same day. All procedures must be performed before the study intervention;
- ∞ Evaluations and collections should take place after 24 hours of administration of the investigational product;
- τ The Informed Consent Form will be obtained by the study nurse directly from the participant, or in case of no possibility of this occurring (example: loss of level of consciousness), from a family member or legal guardian.
- Dx Days of hospitalization after completion of treatment;

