10. STATISTICS

10.1 Analytical plan

Descriptive statistics will be used for demographic, laboratory and clinical data. To assess the safety of the high and the low dosages of CQ the proportion (95% CI) of deaths in each group will be compared with the historical proportion (95% CI) of deaths in patients who did not use CQ in other countries. For qualitative variables, Chi-square tests and Fisher's exact test will be performed. t-test or Mann-Whitney test will be used for means/median comparisons. An cumulative proportion of deaths will be assessed by survival models, using Kaplan-Meier estimate curves. Log-rank and Peto-Peto (correction for low observation numbers in the end of the follow-up) tests will be used for survival time to event analyses.

Statistical analyses will be performed in the R statistical package (v3.6.1), and p<0.05 will be considered significant.

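### Section 10.1 does not say whether the D0 value is used when numeric variables are compared; any between-arm test of laboratory values or viral quantity should adjust for it

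*Protocol*

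**What the plan says.** On method, section 10.1 says "t-test or Mann-Whitney test will be used for means/median comparisons". The sentence names no outcome and does not say whether the value on a given day or the change from D0 is tested. The same section opens with "Descriptive statistics will be used for demographic, laboratory and clinical data". No analysis of covariance, mixed model or other baseline adjustment appears anywhere in the protocol.

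On objectives, section 1.4.2 lists "Alterations in white cell count, hemoglobin, platelets, creatinine, glucose, total bilirubin, ALT and AST over time" and, for virology, "Quantify the virus that causes SARS-CoV2 in oropharyngeal swab, nasal and blood swab samples on days 1, 3, 5, 8, 11, 14" and 28. Both are secondary.

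On data, three rows of Table 1 (section 1.12) are marked as required on D0: "Blood sample collection for hematology and biochemistry", "Blood sample collection for virology and storage" and "Oropharyngeal Swab and Nasal Swab". The notes to the table place D0 procedures before the intervention and D1 collections 24 hours after dosing. D0 is therefore a true baseline and D1 is not.

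**The concern.** A two-sample t-test or Mann-Whitney test on a follow-up value makes no use of a measurement taken from the same patient before treatment. If the two are correlated, part of the between-patient spread at follow-up was already present at entry. It can be removed from the error term without enrolling anyone or adding a visit. An objective worded as alteration over time also implies a reference to the starting value, and a two-sample test at a single day does not supply one.

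What is at stake is the precision of the quantitative comparisons of blood counts, kidney and liver values and viral quantity between doses. The primary comparison is of deaths and is not involved.

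**Working it through.** **The plan's own figure.** The only sample size stated is for mortality: 20% against 10%, 80% power, 5% alpha (section 10.2). Taken as two-sided with unpooled variance, and with unrounded normal quantiles:

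(1.960 + 0.842)² × (0.20×0.80 + 0.10×0.90) / 0.10² = 196.2, so 197 per arm and 394 in all.

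Allowing 10% losses, 394/0.9 = 438, close to the stated 440, which is also 110 blocks of 4. The figure reproduces. It says nothing about laboratory or viral outcomes, for which the protocol gives no SD, effect, power or correlation.

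**Assumptions.** Let ρ be the correlation between the D0 value and the follow-up value, with equal SD at both times. Set the effect so that the unadjusted t-test has 80% power at two-sided 5%. At 197 per arm that effect is (1.960 + 0.842) × √(2/197) = 0.282 SD. Both ρ and the 80% starting point are assumptions, so a range of ρ is shown.

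**Formulas.** Relative to the follow-up value alone, the variance factor is 1 − ρ² with D0 as covariate and 2(1 − ρ) for change from D0. Power is Φ(2.802/√factor − 1.960).

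- ρ = 0.3, covariate: 2.802/√0.91 − 1.960 = 0.977, power 83.6%
- ρ = 0.5, covariate: 2.802/√0.75 − 1.960 = 1.276, power 89.9%
- ρ = 0.7, covariate: 2.802/√0.51 − 1.960 = 1.964, power 97.5%

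| ρ | Follow-up value only | Change from D0 | D0 as covariate | N needed for equal power, covariate vs unadjusted |
|---|---|---|---|---|
| 0.2 | 80% | 60.1% | 81.6% | 0.96 |
| 0.3 | 80% | 65.8% | 83.6% | 0.91 |
| 0.5 | 80% | 80.0% | 89.9% | 0.75 |
| 0.7 | 80% | 95.1% | 97.5% | 0.51 |

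The gains are the same at 100 and 50 per arm when the effect is rescaled to 80% unadjusted power (0.396 and 0.560 SD).

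**Simulation check.** Normal data, 197 per arm, 3000 runs for each ρ:

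| ρ | t-test | Mann-Whitney | Change from D0 | D0 as covariate |
|---|---|---|---|---|
| 0.3 | 80.4% | 78.3% | 66.4% | 83.9% |
| 0.5 | 78.4% | 77.0% | 79.2% | 88.6% |
| 0.7 | 79.0% | 77.3% | 95.3% | 97.4% |

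The simulation agrees with the formulas.

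**The case against.** The other side has a good deal to say, and most of it narrows the point.

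- **The link to these outcomes is inferred.** A reader might infer that 10.1 fixes an unadjusted t-test for laboratory values and viral quantity. It does not: laboratory data are assigned to descriptive statistics in the same section, and the test sentence names no outcome. What remains is conditional. It is the only numeric comparison named, so a between-arm test of these values would fall under it.
- **Change from D0 is not excluded.** A t-test on change satisfies 10.1 and uses D0. At ρ = 0.7 it is nearly as good as covariate adjustment. At ρ = 0.5 it is no better than ignoring D0, and at 0.3 it is worse. That is a reason to state the choice.
- **The tests are valid.** Under randomisation the unadjusted comparison is unbiased. This is about efficiency. Covariates for unpowered secondary outcomes are often left to an analysis plan, which is not at hand. The protocol has, however, named a method, and a better one is available from the data it schedules.
- **Viral quantity at D0 is not promised.** The viral day lists in sections 1.4.2, 3 (Table 2) and 4.1 start at day 1; only Table 1 marks D0. Footnote i describes the blood samples as stored for immune-response work. Patients enter on suspicion, so some viral values may be undetectable, and a log-scale linear model needs a rule for them. This stands, and the fix must allow for it.
- **Follow-up sampling may matter more.** At least some laboratory samples after D0 are optional, footnote h ties laboratory tests to the doctor's request, and procedures stop at discharge. This probably threatens these comparisons more than a missing covariate.

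Two stronger inferences also fail. One is that spread at entry would overwhelm any dose effect; the protocol gives no spread, effect or correlation from which to say so. The other is that a missed kidney or liver difference would be taken as evidence of safety. Section 9.2 bases safety on recorded adverse events and graded laboratory and vital-sign assessments, not on tests of means.

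**Conclusion.** The point holds in a limited form. Section 10.1 leaves the use of D0 unstated and names only two-sample tests, while Table 1 schedules the baseline samples. If these outcomes are compared between arms on follow-up values alone, the power forgone is about 2 to 4 percentage points at ρ of 0.2 to 0.3, 10 at 0.5 and 17 to 18 at 0.7. That rests on an assumed ρ and an assumed 80% starting power. No stated figure is wrong, no test named is invalid and the mortality comparison is untouched. This is a low-priority improvement.

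**What to change.** In section 10.1, state that any between-arm comparison of laboratory values will use a linear model, or a repeated-measures model over the in-hospital days, with arm and the patient's D0 value, on the log scale where skewed. Keep Mann-Whitney as a sensitivity analysis. Add a rule for patients without a D0 value, for example retaining them through the repeated-measures model.

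Use the same model for viral quantity on two conditions: that the D0 samples are quantified, and that a rule is given for values below detection. If either condition is not met, keep a rank-based test.

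The cost is a few sentences, slightly more analysis work and possibly assays of D0 samples that Table 1 already schedules. No added visits or patients are needed. The text should carry a caveat that at least some later laboratory samples are optional and that sampling ends at discharge or death. Baseline adjustment does not cure the selection this causes.

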7. MEASURES TO MINIMIZE BIAS: RANDOMIZATION AND BLINDING

An electronically generated randomization list was prepared by an independent statistician, with 110 blocks of 4 participants per block. This randomization list was generated on R software (Package 'blockrand'). The list will be accessible only to non-blinded pharmacists in the study, in an attempt to minimize observation bias. Participants will be randomized by the study pharmacist to their designated treatment regimen at the time of inclusion and will be subsequently identified throughout the study only by their allocated study number, always assigned following chronological order. In case of SAEs, unmasking will be available to DSMB members, and preliminary analyses will be performed even before the scheduled interim analyses, in order to guide early halting of any of the CQ arms. The randomization and blinding procedure will be described in a specific SOP.

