10.2 Sample calculation and interim analysis

The sample for the primary outcome (reduction in lethality in patients with severe respiratory virus treated with a high dosage of chloroquine compared to a low dosage) was calculated based on the following assumptions:

- 3. The 20% lethality incidence in critically ill patients per year in the low dosage group;
- 4. High dosage chloroquine will be able to reduce lethality by at least 50% compared to low dosage chloroquine;

Thus, considering a test of differences in proportions between 2 groups of the same size, with power of 80% and alpha of 5%, 394 participants will be needed (197 per group). Considering 10% losses, the sample size is 440 participants.

To include interim analyses, we recalculate the sample sizes required in each of the analyzes and in the final analysis, using an alpha-spending function approach, in which the type 1 error is controlled by alpha correction final, based on the alphas used for interim analyses. There are several alpha spending functions and there is always a trade-off between how much will be 'spent' on the interim analysis and the final sample size required. In summary, the more difficult it is to reject the null hypothesis in the interim analysis, the less alpha will be spent and the impact will not be large. We will use Hwang-Shih-DeCani spending functions with $\gamma = -4$ for the upper limit (that is, to interrupt the study that rejects the null hypothesis in the interim analysis), which corresponds to a conservative method, equivalent to the upper limit of O 'Brien-Fleming, with little impact on the final sample size. We will also include a lower limit for testing futility, also using the Hwang-Shih-DeCani spending function, but with a less stringent $\gamma = -2$ parameter for a beta spending function. Although the calculation includes a possible interruption due to futility, this can be ignored, at the discretion of the DSMB (or equivalent) without any impact on the type 1 error.

The table below shows the calculations for the 3 interim analyses and for the final analysis, showing both the sample size required in each analysis as well as the upper (one-tailed 2.5%) and lower limits.

| | | | Superior Limit | | | |
|------------|---|----|----------------|--------|-----|--------------|
| Sample | | | | | | |
| size | | | | p one- | | |
| percentage | | N | Z | tailed | Z | p one-tailed |
| | | 10 | - | 0.278 | 3.1 | |
| 25% | 8 | | 0.59 7 | 6 | | 0.0008 |

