| | | 21 | 0.3 | 0.638 | 2.8 | |
| 50% | 5 | 5 | 6 | 2 | | 0.0024 |
| | | 32 | 1.1 | 0.882 | 2.4 | |
| 75% | 2 | 9 | 1 | 4 | | 0.0074 |
| | | 42 | 2.0 | 0.978 | 2.0 | |
| 100% | 9 | 1 | 0 | 1 | | 0.0220 |

The procedure will be based on the calculation of the Z value of the difference of proportions test in each of the analyses, and the study will continue if this value is between the values of the lower and upper limits and will be interrupted if it is above the upper limit (by rejection H0) or below the lower limit (for futility), remembering that the latter can be ignored without prejudice to the calculations.

All calculations in this report were made in the R environment, version 3.6.1, with the functions implemented in the TrialSize and gsDesign packages. Other intermediary analyzes can be carried out throughout the study to periodically monitor the safety of participants and will provide possible prior information on treatment to the DSMB and Ministry of Health.

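### Section 10.1 sets a blanket p<0.05 that is not reconciled with the corrected final boundary (one-sided 0.0220) that section 10.2 sets for the primary mortality comparison

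*Protocol*

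**What the plan says.** Protocol section 10.1 lists the methods: chi-square and Fisher tests for qualitative variables, t or Mann-Whitney tests for means and medians, and Kaplan-Meier with log-rank and Peto-Peto for deaths over time. It ends with "p<0.05 will be considered significant". No endpoint is exempted and no sidedness is given.

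Protocol section 10.2 starts from a fixed-sample calculation ("with power of 80% and alpha of 5%, 394 participants will be needed (197 per group") and adds three interim analyses by alpha spending, "in which the type 1 error is controlled by alpha correction final, based on the alphas used for interim analyses". The table gives sample sizes "as well as the upper (one-tailed 2.5%) and lower limits". Its last row was broken in extraction ("100% | 9 | 1 | 0 | 1 | | 0.0220"). With the split digits rejoined, it reads N = 429, Z = 2.01, one-sided p 0.0220. The decision at each look rests on the Z of a difference in proportions set against these limits. The futility limit may be disregarded at the monitoring board's discretion.

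Two places allow analyses beyond the four planned looks. Section 7 says that after serious adverse events "preliminary analyses will be performed even before the scheduled interim analyses", to guide the early halting of either dose arm. Section 10.2 adds: "Other intermediary analyzes can be carried out throughout the study", for safety monitoring, with information passing to the DSMB and the Ministry of Health. Neither place gives a number, a boundary or an alpha for these looks.

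**The concern.** The two sections fix different thresholds, and neither refers to the other. Section 10.2 deliberately lowers the final threshold to pay for the interims. Section 10.1, which a reader would take as the analysis plan, gives the uncorrected 0.05 and applies it to a list of tests that includes tests of deaths. If the final two-sided p fell between 0.044 and 0.05, the protocol would support either conclusion on its only primary outcome, and the choice could be made with the result in view.

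This is not a detail left to a statistical analysis plan, because both thresholds are stated in the protocol itself.

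The unscheduled analyses raise a related point. Section 10.1 uses the proportion of deaths as its safety measure, so these looks may examine the same quantity as the primary outcome, and the text does not say that they cannot yield an efficacy conclusion.

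**Working it through.** **Inputs (protocol section 10.2 unless noted).** One-sided alpha 0.025; Hwang-Shih-DeCani spending with γ = −4 for the upper limit; futility by beta spending with γ = −2, non-binding; looks at 25, 50, 75 and 100% of information (section 1.12, note b, gives the same interim timing); rates of 20% and 10%; power 80%.

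**1. Fixed sample size.** With unpooled variance, n per group = (1.960 + 0.842)² × (0.2×0.8 + 0.1×0.9) / 0.1² = 196.2, so 197 per group and 394 in total. This matches the plan.

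**2. Upper boundary.** The spending function is α(t) = 0.025 × (1 − e^{4t}) / (1 − e^{4}), which gives 0.0008, 0.0030, 0.0089 and 0.0250 cumulatively at the four looks. The boundaries were solved by recursive numerical integration with futility ignored.

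| Information | Z | One-sided p, recomputed | One-sided p, plan |
|---|---|---|---|
| 25% | 3.155 | 0.0008 | 0.0008 |
| 50% | 2.818 | 0.0024 | 0.0024 |
| 75% | 2.439 | 0.0074 | 0.0074 |
| 100% | 2.014 | 0.0220 | 0.0220 |

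The inflation factor is 1.087. Multiplied by 394 it gives about 428.4, against 429 in the table. The plan's design is reproduced.

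**3. Both thresholds on one scale.** The final limit is 2 × 0.0220 = 0.044 two-sided. Read as two-sided, the 10.1 threshold is 0.05, or Z = 1.96. The disputed zone is Z from 1.96 to 2.01, that is, two-sided p from 0.044 to 0.05.

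**4. Type I error under each rule.** The interim boundaries stay as tabulated. Each sum adds the null probabilities of first crossing at each look.

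- Final Z = 2.014: 0.0008 + 0.0022 + 0.0059 + 0.0161 = 0.0250.
- Final Z = 1.96, futility ignored: 0.0008 + 0.0022 + 0.0059 + 0.0188 = 0.0277.
- Final Z = 1.96, futility limits always obeyed: 0.0251.

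For the second case the two-sided error is about 0.053 with the plan's one-sided interim limits. It would be 0.0554 only if those limits were mirrored, which the plan does not provide.

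**5. Unscheduled looks (illustration only).** The protocol gives neither times nor thresholds, so these are assumptions. Suppose a look could declare benefit while the planned boundary was kept. One look at 37.5% information at Z ≥ 1.96 gives a one-sided error of 0.042. Three looks at 12.5, 37.5 and 62.5% give 0.068 at Z ≥ 1.96 and 0.0263 at Z ≥ 3. If such looks can stop the trial only for harm of the higher dose, they add nothing to the false-positive rate for benefit.

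**The case against.** The strongest reply is that the specific rule governs the general one. Section 10.2 names the test, applies it at every look including the last, and states how alpha is corrected. The 0.05 in 10.1 is a generic closing line that shares its sentence with the software version. On that reading nothing is inflated. This stands as a reading of intent, and it defeats the stronger inference that the trial's type I error does exceed its stated level: excess arises only if the 10.1 threshold replaces the final 10.2 limit. It does not remove the unqualified wording of 10.1.

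A reader might also infer much larger errors. Setting the table's one-tailed p against 0.05 at the final look gives 5.1% one-sided, and using Z = 1.96 at all four looks gives 6.3%. The document supports neither: it fixes the level as one-tailed 2.5% and tabulates strict interim limits.

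The list of tests in 10.1 is organised by variable type and is not a rival primary test. An uncorrected 2×2 chi-square equals the square of the pooled two-proportion Z.

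On the extra looks, both places describe safety monitoring. Section 9.6 excludes efficacy outcomes from adverse events unless the investigator finds them exceptional, so it would be wrong to say that every death triggers an unblinded analysis. Section 11.9 keeps investigators blind to results. Most of this stands. What remains is that section 7 lets either dose arm be halted. Halting the lower-dose arm for excess deaths comes close to concluding that the higher dose lowers mortality, and no boundary covers that case.

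**Conclusion.** The inconsistency is real and its numerical effect is modest. Sections 10.1 and 10.2 give different final thresholds for the primary comparison, 0.05 against 0.044 on the two-sided scale, and do not say which prevails. The one-sided error is 0.0250 under 10.2. If the 10.1 threshold is used at the final look it lies between about 0.0251 (futility always obeyed) and 0.0277 (futility ignored, the basis on which the plan itself claims control). These figures assume looks at exactly 25, 50, 75 and 100% of information and that 10.1 means a two-sided p.

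The unscheduled looks do not by themselves inflate the error. They leave an efficacy use open, and its size cannot be determined from the document.

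**What to change.** In section 10.1, state that:

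- the primary day-28 mortality comparison is judged only by the difference-of-proportions Z of section 10.2 against its boundaries, with a final one-sided p of at most 0.0220;
- two-sided p<0.05 applies to the other analyses;
- other tests of mortality are supportive.

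In sections 7 and 10.2, state that unscheduled analyses are for safety and cannot support a claim of benefit outside the spending function.

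The cost is a few sentences. The sample size and boundaries do not change. The only downside is a final threshold slightly stricter than the one in 10.1, which 10.2 already intends.
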